**Figure 2: Decision process at Week 52**

The decision process following results of the Week 74 biopsy are described in [Figure 3](#) and as follows: At Week 74, the subject will undergo repeat vulvar punch biopsy/biopsies of the same lesion as study start, but adjacent to the original site within the boundaries of the original lesion (see [Table 3](#)). If after evaluation of biopsy tissue by the PAC there is no evidence of HSIL (Subgroups A or B), the subject will continue to Week 96 for vulvoscopy, and biopsy adjacent to the site of the initial biopsy.

[figure not shown]
If HSIL remains but there is a reduction in lesion size or no change in lesion size from baseline (Subgroups C or D), the Investigator has the option to give the subject a 6th dose of VGX-3100 at Week 78, and the subject will continue on study with vulvoscopy and biopsy at Week 96. Alternatively, the Investigator may choose to treat the subject with surgical or standard treatment, and the subject will continue on study without further biopsy.

**Figure 3: Decision Process at Week 78**

The decision process following results of the Week 74 biopsy are as described in [Figure 4](#) and as follows: At Week 96, the subject will undergo repeat vulvar punch biopsy/biopsies of the same lesion as study start, but adjacent to the original site within the boundaries of the original lesion (see [Table 3](#)). If there is no vulvar HSIL (Subgroups A or B), no further procedures are required. If after evaluation of biopsy tissue by the PAC there is vulvar HSIL (Subgroups C or D), or worsening disease (Subgroup E), the subject will receive surgical or other standard treatment.

**Figure 4: Evaluation process at Week 100**

In the event of worsening disease at any time (ie, Subgroup E – any increase in lesion area from baseline or worsening of HSIL to cancer), the subject will receive surgical treatment per the Investigator's judgement and will continue on study through Week 100 with vulvoscopy, but without further biopsy. For a finding of carcinoma, subjects will receive surgical treatment, and be discontinued from study treatment. The event will be reported as an SAE per [section 7.1.4](#). If wide excision is required, the sample obtained will be sent to the PAC for evaluation.

Definition of Responder and Non-responder:

Responder and non-responder definitions ([Table 4](#)) take into account both histopathologic regression of vulvar HSIL and virologic (HPV-16/18) clearance from tissue samples since HPV persistence is an important factor in the clinical progression of HSIL. A treatment responder is defined as a subject with no histologic evidence of vulvar HSIL and no evidence of HPV-16 or HPV-18 in vulvar tissue at evaluation and who did not receive non-study related medication for treatment of VIN lesions. A treatment non-responder is a subject with histologic evidence of vulvar HSIL, adenocarcinoma-in-situ, or vulvar carcinoma at evaluation, and/or a subject with evidence of HPV-16/18 at evaluation, or a subject who received non-study related medication for treatment of VIN lesions. Any case of histologically confirmed progression from HSIL to carcinoma is considered a non-responder.

Safety Assessment: Subjects will be monitored for:

- 1) Local and systemic events for 7 days following each VGX-3100 dose as noted in the Participant Diary
- 2) All adverse events including SAEs, SUSARs, UADEs, and other unexpected AEs for the duration of the study.

All subjects will be followed for 100 weeks.

Data Safety & Monitoring Board (DSMB): The DSMB will meet quarterly to review safety data. The DSMB will be charged with advising the Sponsor if there appears to be a safety issue. No formal interim analysis is planned. The following stopping rules will be applied:

- If at any time during the study one-third (1/3) or more of the subjects experience an Adverse Event of Special Interest (AESI), further enrollment and study treatment will be halted immediately until a thorough investigation has been conducted by the Medical Monitor, Principal Investigator for the trial, and the DSMB.
- If any SAE (or potentially life-threatening AE) or death assessed as related to study treatment occurs, further enrollment and study treatment will be halted immediately until a thorough investigation has been conducted by the Medical Monitor, Principal Investigator for the trial, IRB (if applicable) and the DSMB.
- If three or more subjects in this study experience the same Grade 3 or 4 adverse event, assessed as related to study treatment, further enrollment and study treatment will be halted immediately until a thorough investigation has been conducted by the Medical Monitor, Principal Investigator for the trial, and the DSMB.
- In the event of two identical, unexpected, Grade 4 toxicities, assessed as related to study treatment, further enrollment and study treatment will be halted immediately until a thorough investigation has been conducted by the Medical Monitor, Principal Investigator for the trial, IRB (if applicable) and the DSMB.

The sponsor or designee will notify all investigators and IRBs/EC (if required) regarding the outcome of any investigation stemming from a Study Pause.

Immunogenicity Assessment: The study will explore humoral and cell mediated immune responses to VGX-3100, and VGX-3100 with imiquimod, in blood samples taken at baseline (both Screening as well as Day 0 prior to dosing) and at Weeks 15, 27, 48, 74 and 96. Vulvar samples will also be analyzed for evidence of immune responses at Screening and at Weeks 48, 74 and 96.

Virologic Assessment: Tissue samples will be obtained to characterize HPV infection at Screening, Week 48, 74 and 96. Cervical samples, oropharyngeal rinse samples, vaginal, and intra-anal tissue swab samples will be obtained to characterize HPV infection in samples from study subjects taken at Screening (cervical sample only), Day 0 prior to dosing (OP, vaginal and intra-anal only) and at Weeks 27, 48, 74, and 96.

If there is residual tissue in the paraffin block after histologic diagnoses have been rendered, then unstained slides and/or the relevant paraffin blocks will be collected for immunohistochemistry (IHC) and in situ hybridization (ISH) for the presence of HPV-16/18. Whenever possible, these studies will be performed on tissue sections from the diagnostic biopsy (pre-dose) and from tissue obtained post-dose (Week 48, 74 and 96).

HLA haplotyping: A sample from one time point during the study will be tested to explore the relationship between subject HLA haplotypes and regression.

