4. Determine the efficacy of four doses of VGX-3100 , alone or in combination with imiquimod, as measured by histologic regression of vulvar HSIL to normal tissue	4. Proportion of subjects with no evidence of vulvar HSIL and no evidence of condyloma on histology (i.e. biopsies or excisional treatment) at the Week 48 visit
5. Determine the efficacy of four doses of VGX-3100 , alone or in combination with imiquimod, as measured by non-progression of vulvar HSIL to vulvar cancer as determined by histology	5. Proportion of subjects with no progression  of vulvar HSIL to vulvar cancer from baseline to Week 48 visit
6. Determine the efficacy of VGX-3100, alone or in combination with imiquimod, as measured by reduction in the surface area of vulvar lesion(s)	6. Percent reduction in the cumulative surface area of the acetowhite vulvar lesion(s) as determined by the quantitative analysis of standardized photographic imaging at Week 48, 74 and 96 compared to baseline  . Results will be classified as: no clinically significant lesion resolution (reduction in lesion area of 0-25%), partial lesion area resolution (>25% and <100% reduction) and complete lesion resolution (no visible lesion).

 No evidence of vulvar HSIL is defined as normal tissue or vulvar LSIL (VIN 1) or condyloma

 Clearance of HPV-16 or HPV-18 is defined as being undetectable by PCR assay.

 Progression is defined as advancement to carcinoma by histology according to the Pathology Adjudication Committee.

 Digital photos will be analyzed with a computer program to calculate the total lesion size in cm^2.

7. Describe the humoral and cellular immune response to VGX-3100, administered alone or in combination with imiquimod, post dose 3, post dose 4, and after additional dosing
	
7a. Levels of serum anti-HPV-16 and anti-HPV-18 antibody concentrations at baseline, Weeks 15, 27, 48, 74 and 96 visits 7b. Interferon-<math>\gamma</math> ELISpot response magnitudes at baseline and Weeks 15, 27, 48, 74 and 96 visits 7c. Flow Cytometry response magnitudes at baseline and Week 27 visits

Exploratory Objectives
	
Associated Exploratory Endpoints

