**Figure 1: Study Visit Schedule**

**Imiquimod treatment** - Subjects randomized to the VGX-3100 with imiquimod arm will apply imiquimod 5% cream to the vulvar lesion(s) beginning in the evening on Day 0, and will continue to apply imiquimod cream three times per week for 20 weeks (inclusive of administration in the evening of VGX-3100 dosing). Subjects unable to tolerate imiquimod treatment may reduce their dosing frequency, and will document their use on the imiquimod dosing log provided.

**Efficacy Assessment:** Biopsies obtained as part of the study at Screening will be from the region of most advanced and severe disease as judged by the Investigator, and must be a minimum of 4 mm in length. Visible lesion must remain after screening biopsy to ensure measurement on study.

[figure not shown]
Visualization of a normal appearing vulva by visual inspection with vulvoscopy is insufficient evidence to confirm disease regression. Disease regression will be based on histopathologic assessment at Week 48, 74, and 96. Subjects will be monitored during the course of the study by vulvoscopy. Lesion(s), defined as areas that stain acetowhite, will be assessed during vulvoscopy at Screening, Day 0, and Weeks 4, 12, 27, 48, 74 and 96. Using standardized high resolution digital imaging, vulvar lesion(s) will also be quantitatively measured at Screening, Day 0, and Weeks 4, 12, 27, 48, 74 and 96.

The decision process following results of the Week 48 biopsy are described in [Figure 2](#) below and as follows: At Week 48, the subject will undergo repeat vulvar punch biopsy/biopsies of the same lesion as study start, but adjacent to the original site within the boundaries of the original lesion (see [Table 3](#) for Minimally Required Biopsy Procedures). If after evaluation of biopsy tissue by the PAC there is no evidence of HSIL (Subgroups A or B), the subject will continue to Week 74 for vulvoscopy, and biopsy adjacent to the site of the initial biopsy. Repeat biopsies that are indicated beyond Week 48 must be taken from the same lesion, adjacent to the prior biopsy site(s) within the boundaries of the original lesion.

If after evaluation of the biopsy tissue HSIL remains, but there is a reduction in lesion size or no change in lesion size from baseline (Subgroups C or D), the Investigator has the option to give the subject a 5th dose of VGX-3100 at Week 52, and the subject will continue on study with vulvoscopy and biopsy at

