#### 3.1 TREATMENT REGIMENS

All eligible subjects who consent to participate in the study will receive four doses of 6 mg of VGX-3100 administered by IM injection followed by EP. The first dose will be administered as soon as possible following confirmation of the HSIL diagnosis, HPV-16/18 status and all other eligibility criteria but no more than 10 weeks following collection of the subject's biopsy specimen used for diagnosis by the PAC.

Each dose of VGX-3100 will be administered in a 1 mL volume IM (deltoid, preferred site, or anterolateral quadriceps, alternate site) followed immediately by EP with the CELLECTRA® 2000 device. As shown in [Figure 1](#), study subjects will receive at least 4 doses of VGX-3100 and potentially a 5th and 6th dose depending upon their disposition with regard to histologic and lesion area changes. The first dose will be administered on Day 0, the second at Week 4, the third at Week 12, and the fourth dose will be administered at Week 24. Subjects with no HSIL at Week 48 (Subgroups A and B) will receive 4 doses. Subjects with HSIL at Week 48, who have a reduction in lesion size or no increase in lesion size from baseline (Subgroups C or D), may receive a fifth dose of VGX-3100 administered IM with EP at Week 52 per the judgment of the Investigator. Subjects with HSIL at Week 74, who have a reduction in lesion size or no increase in

lesion size from baseline (Subgroups C or D), may receive a sixth dose of VGX-3100 administered IM with EP at Week 78 per the judgment of the Investigator. Subjects in Subgroup E should receive surgical treatment per the judgement of the Investigator. All subjects will complete the study at Week 100.

Imiquimod treatment - Subjects randomized to the VGX-3100 with imiquimod arm will apply imiquimod 5% cream to the vulvar lesion beginning in the evening on Day 0, and will continue to apply treatment three times per week for 20 weeks (inclusive of administration in the evening of VGX-3100 dosing). Subjects unable to tolerate imiquimod treatment may reduce their dosing frequency, and will document their use on the imiquimod dosing log provided.

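### Subgroup E begins at any measured rise in lesion area, so at the Week 48 or Week 74 decision a stable lesion with HSIL has about an even chance of being classed as worsening

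*Protocol*

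**What the plan says.** **Sorting rule.** At Week 48 and again at Week 74, women with persistent HSIL are sorted by lesion size.

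- For dose 5, the synopsis keeps a woman eligible on these terms: "there is a reduction in lesion size or no change in lesion size from baseline (Subgroups C or D), the Investigator has the option". It repeats the rule for dose 6: "If HSIL remains but there is a reduction in lesion size or no change in lesion size from baseline (Subgroups C or D").
- Section 3.1 words it as not increased rather than unchanged: "Subjects with HSIL at Week 48, who have a reduction in lesion size or no increase in lesion size from baseline (Subgroups C or D").
- Subgroup E is "any increase in lesion area from baseline or worsening of HSIL to cancer" (synopsis after Figure 4; Section 3.2).

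**Measurement.** Lesions "will also be quantitatively measured at Screening, Day 0, and Weeks 4, 12, 27, 48, 74 and 96". A synopsis note to secondary endpoint 6 says: "Digital photos will be analyzed with a computer program to calculate the total lesion size", in cm². The same endpoint counts a small fall as "no clinically significant lesion resolution (reduction in lesion area of 0-25"%).

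**Consequences.** Section 6.4 reserves the Week 52 and Week 78 doses for Subgroups C and D. A woman in Subgroup E has surgery at the Investigator's judgement and "will continue on study through Week 100 with vulvoscopy, but without further biopsy".

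**Week 48 biopsy.** Table 1, footnote i, limits the Week 74 and 96 biopsies to Subgroups C and D but puts no such limit on Week 48. Inclusion criterion 6 describes the Week 48 excision or biopsy as required, and Section 6.2.10 lists it without exception.

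**Analysis set.** In Version 1.1, Section 8.4 restricts the mITT set to treated women who have the endpoint, and Section 8.11.6 rules out imputation. Section 8 of Version 1.2 is not visible.

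**The concern.** On a continuous scale a lesion almost never measures exactly the same twice, so the unchanged category that the protocol wants to keep eligible is effectively empty. A stable lesion reads either slightly smaller (C/D, further dose possible, Week 74 or 96 histology) or slightly larger (E, neither). Two women in the same clinical state can be managed in opposite ways because of reading error, in a study whose stated aim is to avoid or minimize surgery. The women who supply histology after five or six doses would also be selected partly by that error.

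The second matter is a conflict in the text. The synopsis lets Subgroup E arise at any time and then stops biopsies, while other places treat the Week 48 biopsy as required of everyone. If the first reading is applied, women judged to be worsening before Week 48 have no primary endpoint and disappear from the denominator instead of counting as failures.

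**Working it through.** The protocol states no measurement error, tolerance or misclassification rate, so there is no figure to reproduce.

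**Step 1: unchanged lesion, one decision, no margin.** Let B be the baseline reading and F the follow-up reading, with the same true area and independent, identically distributed continuous errors. By exchangeability P(F > B) = 1/2. The precision of the imaging does not enter. A single Week 48 or Week 74 decision, taken alone, therefore puts 50% of stable lesions in Subgroup E.

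**Step 2: both decisions.** Weeks 48 and 74 share one baseline. A stable lesion passes both only if the baseline is the largest of three exchangeable readings: 1/3. Given a pass at Week 48, the chance of being classed E at Week 74 is 1 − (1/3)/(1/2) = 1/3.

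**Step 3: other true changes, and the effect of a margin.** Assume lognormal error with a coefficient of variation (CV) per reading. No CV is given in the document; 5%, 10% and 20% are assumptions. For true relative change d and margin t:

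P(classed E) = 1 − Φ( [ln(1+t) − ln(1+d)] / (CV × √2) )

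| True change | Margin | CV 5% | CV 10% | CV 20% |
|---|---|---|---|---|
| none | 0 | 50% | 50% | 50% |
| none | 10% | 8.9% | 25.0% | 36.8% |
| none | 25% | 0.1% | 5.7% | 21.5% |
| 10% smaller | 0 | 6.8% | 22.8% | 35.5% |
| 20% larger | 0 | 99.5% | 90% | 74% |
| 20% larger | 25% | 28% | 39% | 44% |
| 50% larger | 25% | 99.5% | 90% | 74% |

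Example: 20% larger, margin 25%, CV 5%: ln(1.25/1.20) = 0.0408; 0.0408/0.0707 = 0.577; 1 − Φ(0.577) = 0.28.

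**Step 4: the denominator, if an early Subgroup E woman has no Week 48 tissue.** Removing non-responders raises the proportion. For illustration, 3 responders among 24 is 12.5%; drop two non-responders and 3 among 22 is 13.6%. The exact one-sided test against 2% at 0.025 needs 3 responders for 21 to 24 women and 2 responders for 10 to 12, so small losses within those ranges bias the estimate and its interval without changing whether superiority is declared.

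**The case against.** **The figures are missing.** Figures 2 to 4 describe the decision process, and the visible text never separates C from D, so they hold detail that cannot be checked. They may define how an unchanged lesion is determined. This stands as a limit. A convention found there would still need to be reconciled with the running text, which says any increase in two places.

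**The measure is not tied to the rule.** No sentence says that the photographic area drives the sorting; the computation note belongs to an efficacy endpoint, and lesions are also viewed at vulvoscopy. True, but Subgroup E is worded in terms of area, and this is the only area measurement described.

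**The stakes are modest.** This stands. Doses 5 and 6 are optional even within C/D, where the Investigator may choose surgery and end biopsies too. The extended-dosing endpoints are exploratory. At Week 96, C, D and E are handled alike.

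**Zero tolerance may be deliberate caution.** Section 1.1.8 names delayed treatment as a risk, and withholding more investigational doses from women with growing lesions is defensible. The 0 to 25% band grades efficacy and is not a safety threshold. Both stand, so 25% is only an example. The same section says the disease typically takes years to progress, which weakens the case for having no margin at all.

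**Stronger readings.** A reader might infer from the synopsis's at-any-time phrase that every interim photograph is tested against the rule, so that 75% of stable lesions are classed E by Week 27 and 80% by Week 48. No sentence says that the Week 4, 12 and 27 measurements are used this way, Section 3.2 omits the phrase, and the subgroups otherwise appear as outcomes of the Week 48, 74 and 96 decisions. A reader might also infer that early Subgroup E women certainly lose the Week 48 biopsy; footnote i, inclusion criterion 6 and Section 6.2.10 point the other way. Nor does reading error force surgery, which is left to judgement throughout.

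**Conclusion.** The point holds in a limited form. At a Week 48 or Week 74 decision, a woman with HSIL and a truly unchanged lesion has about a 50% chance of being classed as worsening, which closes the optional further dose and the later biopsy. The 50% needs only like, independent errors at baseline and follow-up; every figure for a real change or a margin also rests on an assumed CV. The number of women with stable lesions is not given, so no count is claimed. The sorting rule at these decisions does not reach the primary endpoint.

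The Week 48 biopsy conflict is separate and is an ambiguity, not an established loss. If resolved the wrong way it favours the treatment by removing failures, subject to Version 1.1's analysis rules still applying.

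**What to change.** 1. In the synopsis and Section 3.2, define Subgroup E as an increase in area above a prespecified imaging-repeatability margin (for example more than 25%, or a smaller margin set from repeat readings), or progression to cancer. Define C/D as HSIL without such an increase, in the same words everywhere. Keep the Investigator's freedom to biopsy or operate at any time. Repeat readings of one photograph miss variation in image capture, so the margin should allow for that as well.
2. State that a woman classed E or treated surgically before Week 48 still has the Week 48 biopsy where possible, and in any case counts as a non-responder in the primary analysis.

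**Cost.** Wording changes, plus repeat readings if they are used to set the margin; no added visits or patients. The real price is sensitivity: with a 25% margin, true growth of 20% is flagged at one reading in about 28% to 44% of cases (CV 5% to 20%), against 99.5% to 74% now. The Investigator's option of surgery within C/D offsets this, and a smaller margin reduces it at the price of more false classifications of stable lesions.

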**Study Population:**

Inclusion:

1. Must understand, agree and be able to comply with the requirements of the protocol. Subjects must be willing and able to provide voluntary consent to participate and sign a Consent Form prior to study-related activities;
2. Women aged 18 and above;
3. Confirmed vulvar infection with HPV types 16 and/or 18 at screening;
4. Vulvar tissue specimen/slides provided to the Study Pathology Adjudication Committee for diagnosis must be collected within 10 weeks prior to anticipated date of first dose of study drug;
5. Histologic evidence of vulvar HSIL as confirmed by the PAC at screening;
6. Must be judged by investigator to be an appropriate candidate for the protocol-specified procedure (i.e. excision or biopsy) required at Week 48;
7. Must have vulvar HSIL that is accessible for sampling by biopsy instrument and of adequate size to ensure that a visible lesion remains after 4 mm screening biopsy;
8. Must have vulvar HSIL that can be completely demarcated for area measurement;
9. Must meet one of the following criteria with respect to their reproductive capacity:
  - a) Is post-menopausal as defined by spontaneous amenorrhea for more than 12 months or spontaneous amenorrhea for 6-12 months with FSH level >40 mIU/mL;
  - b) Is surgically sterile due to absence of ovaries or due to a bilateral tubal ligation/occlusion performed more than 12 months prior to screening;
  - c) Women of Child Bearing Potential (WOCBP) are willing to use a contraceptive method with failure rate of less than 1% per year when used consistently and correctly from screening until 6 months following the last dose of investigational product. Acceptable methods are the following:
    - i) Hormonal contraception: either combined or progestin-alone including oral contraceptives, injectable, implants, vaginal ring, or percutaneous patches. Hormonal contraceptives must not be used in subjects with a history of hypercoagulability (e.g., deep vein thrombosis, pulmonary embolism);
    - ii) Abstinence from penile-vaginal intercourse when this is the subject's preferred and usual lifestyle;
    - iii) Intrauterine device or intrauterine system;
    - iv) Male partner sterilization at least 6 months prior to the female subject's entry into the study, and this male is the sole partner for that subject.
10. Has normal screening electrocardiogram (ECG) or screening ECG with no clinically significant findings as judged by the investigator.

Exclusion:

- 1) Untreated microinvasive or invasive cancer;
- 2) Biopsy-proven Vaginal Intraepithelial Neoplasia (VAIN) and are not undergoing treatment for VAIN;
- 3) Biopsy-proven Anal Intraepithelial Neoplasia (AIN) and are not undergoing treatment for AIN;
- 4) Biopsy-proven Cervical Intraepithelial Neoplasia (CIN) 2/3 and are not undergoing treatment for CIN;
- 5) Biopsy-proven differentiated VIN;
- 6) More than 10 weeks have elapsed between date of initial tissue biopsy for screening and day of first dose (i.e. Day 0);
- 7) Vulvar HSIL that is not accessible for sampling by biopsy instrument;
- 8) Vulvar HSIL that is not of adequate size to ensure that a visible lesion remains after biopsy;
- 9) Cervical lesion(s) that cannot be fully visualized on colposcopy due to extension high into cervical canal at screening;
- 10) History of endocervical curettage (ECC) which showed cervical HSIL indeterminate, or insufficient for diagnosis (ECC is not performed as part of study screening) and did not receive definitive treatment;
- 11) Treatment for genital warts within 4 weeks prior to screening;
- 12) Any previous treatment for vulvar HSIL (e.g. with surgery and/or imiquimod) within 4 weeks prior to screening;
- 13) Allergy to imiquimod 5% cream or to an inactive ingredient in imiquimod 5% cream;
- 14) Is pregnant, breastfeeding or considering becoming pregnant within 6 months following the last dose of investigational product;
- 15) Presence of any abnormal clinical laboratory values greater than Grade 1 per Common Toxicity Criteria for Adverse Events (CTCAE) v 4.03 within 30 days prior to Day 0 **or** less than Grade 1 but deemed clinically significant by the investigator;
- 16) Immunosuppression as a result of underlying illness or treatment including:
  - a) History of or positive serologic test for HIV at screening;
  - b) Primary immunodeficiencies;
  - c) Long term use ( $\geq 7$  days) of oral or parenteral glucocorticoids at a dose of  $\geq 20$  mg/day of prednisone equivalent (use of inhaled, nasal, otic, and ophthalmic corticosteroids are allowed);
  - d) Current or anticipated use of disease modifying doses of anti-rheumatic drugs (e.g., azathioprine, cyclophosphamide, cyclosporine, methotrexate) and biologic disease modifying drugs such as TNF- $\alpha$  inhibitors (e.g. infliximab, adalimumab or etanercept);
  - e) History of solid organ or bone marrow transplantation;
  - f) Any prior history of other clinically significant immunosuppressive or clinically diagnosed autoimmune disease that may jeopardize the safety of the subject or require therapy that would interfere with study assessments or endpoint evaluation, or otherwise impact the validity of the study results.
- 17) History of previous therapeutic HPV vaccination (licensed prophylactic HPV vaccines are allowed, e.g. Gardasil®9, Gardasil®, Cervarix®);
- 18) Received any non-study related non-live vaccine within 2 weeks of Day 0;
- 19) Received any non-study related live vaccine (e.g. measles vaccine) within 4 weeks of Day 0;
- 20) Significant acute or chronic medical illness that could be negatively impacted by the electroporation treatment as deemed by the investigator;
- 21) Current or history of clinically significant, medically unstable disease which, in the judgement of the investigator, would jeopardize the safety of the subject, interfere with study assessments or endpoint evaluation, or otherwise impact the validity of the study results (e.g. chronic renal failure, angina, myocardial ischemia or infarction, class 3 or higher congestive heart failure, cardiomyopathy, or clinically significant arrhythmias);
- 22) Malignancy or treatment for malignancy within 2 years of screening, with the exception of superficial

- skin cancers that only require local excision;
- 23) Acute or chronic bleeding or clotting disorder that would contraindicate IM injections or use of blood thinners (e.g. anticoagulants or antiplatelet drugs) within 2 weeks of Day 0;
  - 24) History of seizures unless seizure free for 5 years with the use of one or fewer antiepileptic agents;
  - 25) Sustained, manually confirmed, sitting systolic blood pressure >150 mm Hg or <90 mm Hg or a diastolic blood pressure >95 mm Hg at Screening or Day 0;
  - 26) Resting heart rate <50 bpm (unless attributable to athletic conditioning) or >100 bpm at Screening or Day 0;
  - 27) Prior major surgery within 4 weeks of Day 0;
  - 28) Participated in an interventional study with an investigational compound or device within 4 weeks of signing informed consent (participation in an observational study is permitted);
  - 29) Less than two acceptable sites available for IM injection considering the deltoid and anterolateral quadriceps muscles;
  - 30) Tattoos, keloids or hypertrophic scars located within 2 cm of intended treatment site;
  - 31) Cardioverter-defibrillator or pacemaker (to prevent a life-threatening arrhythmia) that is located in ipsilateral deltoid injection site (unless deemed acceptable by a cardiologist);
  - 32) Metal implants or implantable medical device within the intended treatment site (i.e. electroporation area);
  - 33) Active drug or alcohol use or dependence that, in the opinion of the investigator, would interfere with adherence to study requirements;
  - 34) Prisoner or subject who is compulsorily detained (involuntarily incarcerated) for treatment of either a psychiatric or physical (i.e. infectious disease) illness;
  - 35) Active military service personnel;
  - 36) Study-related staff or family members of study-related staff;
  - 37) Any illness or condition that in the opinion of the investigator may affect the safety of the subject or the evaluation of any study endpoint.

